12. ADVERSE EVENT REPORTING

Timely, accurate, and complete reporting and analysis of safety information from clinical studies are crucial for the protection of subjects, investigators, and the sponsor, and are mandated by

regulatory agencies worldwide. The sponsor has established Standard Operating Procedures in conformity with regulatory requirements worldwide to ensure appropriate reporting of safety information; all clinical studies conducted by the sponsor or its affiliates will be conducted in accordance with those procedures.

12.1. Definitions

12.1.1. Adverse Event Definitions and Classifications

Adverse Event

An adverse event is any untoward medical occurrence in a clinical study subject administered a medicinal (investigational or non-investigational) product. An adverse event does not necessarily have a causal relationship with the treatment. An adverse event can therefore be any unfavorable and unintended sign (including an abnormal finding), symptom, or disease temporally associated with the use of a medicinal (investigational or non-investigational) product, whether or not related to that medicinal (investigational or non-investigational) product. (Definition per ICH)

This includes any occurrence that is new in onset or aggravated in severity or frequency from the baseline condition, or abnormal results of diagnostic procedures, including laboratory test abnormalities.

Note: The sponsor collects adverse events starting with the signing of the ICF (see Section 12.3.1, All Adverse Events, for time of last adverse event recording).

Serious Adverse Event

A serious adverse event based on ICH and EU Guidelines on Pharmacovigilance for Medicinal Products for Human Use is any untoward medical occurrence that at any dose:

- Results in death
- Is life-threatening
(The subject was at risk of death at the time of the event. It does not refer to an event that hypothetically might have caused death if it were more severe.)
- Requires inpatient hospitalization or prolongation of existing hospitalization
- Results in persistent or significant disability/incapacity
- Is a congenital anomaly/birth defect
- Is a suspected transmission of any infectious agent via a medicinal product
- Is Medically Important*

* Medical and scientific judgment should be exercised in deciding whether expedited reporting is also appropriate in other situations, such as important medical events that may not be immediately life threatening or result in death or hospitalization but may jeopardize the subject or may require intervention to prevent one of the other outcomes listed in the definition above. These should usually be considered serious.

If a serious and unexpected adverse event occurs for which there is evidence suggesting a causal relationship between the study vaccine and the event (eg, death from anaphylaxis), the event must be reported as a serious, unexpected suspected adverse reaction (SUSAR) (even after the study is over, if the sponsor, DRC or investigator becomes aware of them) by the sponsor to the Health Authorities and by the investigator to the IRB/IEC according to regulatory and local requirements.

Unlisted (Unexpected) Adverse Event/Reference Safety Information

An adverse event is considered unlisted if the nature or severity is not consistent with the applicable product reference safety information. For Ad26.ZEBOV and for MVA-BN-Filo, the expectedness of an adverse event will be determined by whether or not it is listed in the respective Investigator's Brochures and Addenda, if applicable.^{12,13,14} For MVA-BN-Filo, for reporting purposes, all increases of troponin I will be considered unlisted.

Adverse Event Associated With the Use of the Study Vaccine

An adverse event is considered associated with the use of the study vaccine if the attribution is possibly, probably or very likely by the definitions listed in Section 12.1.2.

An adverse event is considered not associated with the use of the study vaccine if the attribution is not related or doubtful by the definitions listed in Section 12.1.2.

Adverse Events of Special Interest

Although not a single case of confirmed myocarditis and/or pericarditis has been reported to date following MVA-BN vaccination, due to particular concerns associated with traditional smallpox vaccines, the following adverse events of special interest are defined and must be reported to the appropriate sponsor contact person by study-site personnel within 24 hours of their knowledge of the event:

- Any cardiac sign or symptom developed since the prime vaccination
- ECG changes determined to be clinically significant

Any of the above will trigger investigation of troponin I and an increase of troponin I ≥ 2 x institutional upper limit of normal will be also considered adverse events of special interest.

Troponin I increase will always be considered unexpected for regulatory purposes in the current study.

12.1.2. Attribution Definitions

Every effort should be made by the investigator to explain any adverse event and to assess its potential causal relationship, ie, to administration of the study vaccine or to alternative causes (eg, natural history of an underlying diseases, concomitant therapies). This applies to all adverse events, whether serious or non-serious.

The investigator will use the following guidelines to assess the causal relationship of an adverse event to study vaccine:

Not Related

An adverse event that is not related to the use of study vaccine.

Doubtful

An adverse event for which an alternative explanation is more likely, eg, concomitant drug(s), concomitant disease(s), or the relationship in time suggests that a causal relationship is unlikely.

Possible

An adverse event that might be due to the use of study vaccine. An alternative explanation, eg, concomitant drug(s), concomitant disease(s), is inconclusive. The relationship in time is reasonable; therefore, the causal relationship cannot be excluded.

Probable

An adverse event that might be due to the use of study vaccine. The relationship in time is suggestive (eg, confirmed by dechallenge). An alternative explanation, eg, concomitant drug(s), concomitant disease(s), is less likely.

Very Likely

An adverse event that is listed as a possible adverse reaction and cannot be reasonably explained by an alternative explanation, eg, concomitant drug(s), concomitant disease(s). The relationship in time is very suggestive.

12.1.3. Severity Criteria

Adverse events and laboratory data will be coded for severity using the toxicity grading tables in [Attachment 1](#). For adverse events not identified in the table, the following guidelines will apply:

Mild	Grade 1	Symptoms causing no or minimal interference with usual social and functional activities
Moderate	Grade 2	Symptoms causing greater than minimal interference with usual social and functional activities
Severe	Grade 3	Symptoms causing inability to perform usual social and functional activities

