11.8. Pausing Rules

The Principal Investigator and the designated co-investigators will review the safety of enrolled subjects on an ongoing basis.

If any pausing rule is met, and following an internal safety review it is deemed appropriate to restart dosing, a request to restart dosing with pertinent data must be submitted to health authorities as a request for a substantial amendment. Communications from the DRC will be forwarded by the investigator to the IRB/IEC and by the sponsor to relevant health authorities.

The following pausing rules apply to the Sentinel Cohorts. These pausing rules will prevent the start of enrollment of Cohort 1 and will trigger a DRC meeting:

1. One subject experiences anaphylaxis or generalized urticaria clearly attributable to study vaccination within 24 hours of the prime vaccination; *OR*
2. One subject experiences a serious adverse event that is considered to be related to any of the study vaccines; *OR*
3. One subject experiences a severe (grade 3) unsolicited adverse event that is considered to be related to any of the study vaccines; *OR*
4. One subject experiences a severe (grade 3) solicited injection site reaction. (The size [measured in mm] of erythema will not be used as a pausing criterion); *OR*
5. One subject experiences a severe (grade 3) solicited systemic adverse event considered to be related to any of the study vaccines. (Subjective systemic adverse event corroborated by study personnel.); *OR*
6. Death of a subject.

The following pausing rules apply to Cohort 1 of any group in the main study. These pausing rules will prevent the start of enrollment of Cohort 2 and will trigger a DRC meeting:

1. One subject experiences anaphylaxis or generalized urticaria clearly attributable to study vaccination within 24 hours of prime vaccination; *OR*
2. One subject experiences a serious adverse event that is considered to be related to any of the study vaccines; *OR*
3. One subject experiences a severe (grade 3) unsolicited adverse event that is considered to be related to any of the study vaccines; *OR*
4. One subject experiences a severe (grade 3) solicited injection site reaction. (The size [measured in mm] of erythema will not be used as a pausing criterion); *OR*
5. One subject experiences a severe (grade 3) solicited systemic adverse event considered to be related to any of the study vaccines. (Subjective systemic adverse event corroborated by study personnel.); *OR*
6. Death of a subject.

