Occurrence of any of the following events after initiation of Cohort 2 in any group in the main study will lead to suspension of further study vaccination in both the main and the substudy, and will trigger a meeting of the DRC to discuss study suspension or discontinuation of further vaccination:

1. One or more subjects experience a serious adverse event that is considered to be related to any of the study vaccines; *OR*
2. One or more subjects experience anaphylaxis or generalized urticaria clearly attributable to vaccination with study vaccine; *OR*
3. Two or more subjects experience a severe (grade 3) (non-serious) unsolicited adverse event that is considered to be related to any of the study vaccines; *OR*
4. Two or more subjects experience a severe (grade 3) (non-serious) laboratory abnormality (including unexplained hematuria) considered to be related to any of the study vaccines; *OR*
5. Two or more subjects who received at least one dose of study vaccine to date experience the same severe (grade 3) (non-serious) solicited injection site reaction. (The size [measured in mm] of erythema will not be used as a pausing criterion); *OR*
6. Two or more subjects who received at least one dose of study vaccine to date experience the same severe (grade 3) (non-serious) solicited systemic adverse event considered to be related to any of the study vaccines. (Subjective systemic adverse event corroborated by study personnel.); *OR*
7. Death of a subject.

For the events described above, the investigator notifies the sponsor's study responsible physician (or designee) immediately, and in all cases within 24 hours at the latest after the site observes, or

is notified of, the adverse events, and the study responsible physician (or contacted sponsor's representative) then notifies the DRC immediately. A thorough analysis of all grade 3 cases will be carried out by the investigator with the study responsible physician, irrespective of whether the criteria for pausing the study are met. If the case(s) is (are) deemed to meet the pausing rules, specified above, the DRC will convene within 3 business days to review these adverse events.

A subject will not be given the boost vaccination if he/she experiences:

1. Anaphylaxis clearly attributable to vaccination with study vaccine; *OR*
2. Generalized urticaria considered to be related to any of the study vaccines within 72 hours after administration of a study vaccine; *OR*

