3. A serious adverse event that is considered to be related to any of the study vaccines; *OR*
4. A severe (grade 3) (non-serious) laboratory abnormality (including unexplained hematuria) that is considered to be related to any of the study vaccines; *OR*
5. A severe (grade 3) (non-serious) unsolicited adverse event that is considered to be related to any of the study vaccines; *OR*
6. A severe (grade 3) (non-serious) solicited injection site reaction that does not recover within 48 hours, *OR*
7. A severe (grade 3) (non-serious) solicited systemic adverse event considered to be related to any of the study vaccines that does not recover within 48 hours.

Vaccinations for an individual subject may be suspended for safety concerns other than those described above, at the discretion of the investigator if he/she feels the subject's safety may be threatened. The investigator may ask for a review meeting to be held for any single event or combination of multiple events which, in his/her professional opinion, jeopardize the safety of the subjects or the reliability of the data.

Vaccinations for the study may be suspended for safety concerns other than those described above or before pausing rules are met if in the judgment of investigator, subject safety may be threatened. The sponsor should be notified that the DRC will need to be convened.

If a pause is installed, vaccinations will be held until DRC review is complete. Resumption of vaccination may be determined by the DRC following cumulative review of the available safety data as outlined in the charter. The site will be allowed to resume activities upon receipt of a written notification from the sponsor. As applicable, the appropriate regulatory authorities will be informed in writing of the decision by the DRC to resume or discontinue study activities. The site is responsible for notifying their IRB/IEC according to local standards and regulations. The sponsor is responsible for notifying the regulatory authorities.

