Vomiting	No interference with activity or 1-2 episodes/24 hours	Some interference with activity or >2 episodes/24 hours	Prevents daily activity or requires IV hydration
Diarrhea	2-3 loose or watery stools or <400 g/24 hours	4-5 loose or watery stools or 400-800 g/24 hours	6 or more loose or watery stools or >800 g/24 hours or requires IV hydration
Reactogenicity	Mild (Grade 1)	Moderate (Grade 2)	Severe (Grade 3)
Local reactions			
Pain	Does not interfere with activity	Repeated use of non-narcotic pain reliever >24 hours or interferes with activity	Any use of narcotic pain reliever or prevents daily activity
Tenderness	Discomfort only to touch	Discomfort with movement	Significant discomfort at rest
Erythema/redness ^a	2.5-5 cm	5.1-10 cm	>10 cm
Induration/swelling ^b	2.5-5 cm and does not interfere with activity	5.1-10 cm or interferes with activity	>10 cm or prevents daily activity
Systemic reactions			
Allergic reaction	Pruritus without rash	Localized urticaria	Generalized urticaria; angioedema or anaphylaxis
Headache	No interference with activity	Repeated use of non-narcotic pain reliever >24 hours or some interference with activity	Significant; any use of narcotic pain reliever or prevents daily activity
Fatigue	No interference with activity	Some interference with activity	Significant; prevents daily activity
Myalgia	No interference with activity	Some interference with activity	Significant; prevents daily activity
All other conditions	Mild (Grade 1)	Moderate (Grade 2)	Severe (Grade 3)
Illness or clinical adverse event (as defined according to applicable regulations)	No interference with activity	Some interference with activity not requiring medical intervention	Prevents daily activity and requires medical intervention

^a In addition to grading the measured local reaction at the greatest single diameter, the measurement should be recorded as a continuous variable.

^b Induration/swelling should be evaluated and graded using the functional scale as well as the actual measurement.

LABORATORY AND VITAL SIGNS TOXICITY GRADING

Blood, Serum, or Plasma Chemistries ^{a,b}	LO/Hi/N ^c	Mild (Grade 1) ^d	Moderate (Grade 2)	Severe (Grade 3)
Sodium (mEq/L or mmol/L)	LO	132-<LLN	130-131	<130
	HI	>ULN-148	149-150	>150
Potassium (mEq/L or mmol/L)	LO	>ULN-3.1	<3.1-3.0	<3.0
	HI	>ULN-5.2	5.3-5.4	>5.4
Glucose (mg/dL)	LO	65-67	55-64	<55
	HI ^e	>ULN-120	121-130	>130
	HI ^f	140-159	160-200	>200

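### Section 12.1.3 and the catch-all row of Attachment 1 define Grade 3 differently for adverse events without a named row, so the Grade 3 pausing and boost rules are ambiguous for those events

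*Protocol*

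**What the plan says.** Section 12.1.3 of the protocol sends severity grading of adverse events and laboratory data to the tables in Attachment 1. It then adds: "For adverse events not identified in the table, the following guidelines will apply". On that scale Grade 3 is "Symptoms causing inability to perform usual social and functional activities".

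The last row of the clinical tables in Attachment 1, under All other conditions, is labelled "Illness or clinical adverse event (as defined according to applicable regulations"). Its Grade 2 is "Some interference with activity not requiring medical intervention" and its Grade 3 is "Prevents daily activity and requires medical intervention".

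Section 11.8 relies on Grade 3 without defining it:

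- **Sentinel Cohorts and Cohort 1:** the next cohort does not start if "One subject experiences a severe (grade 3) unsolicited adverse event that is considered to be related to any of the study vaccines". One Grade 3 injection site reaction, or one related Grade 3 solicited systemic event, has the same effect.
- **After Cohort 2 starts:** vaccination is suspended in the main study and the substudy if "Two or more subjects experience a severe (grade 3) (non-serious) unsolicited adverse event" considered related. For solicited reactions, two subjects must have the same event.
- **Individual boost:** it is withheld after "A severe (grade 3) (non-serious) unsolicited adverse event that is considered to be related to any of the study vaccines". Solicited Grade 3 events withhold it only if they have not recovered within 48 hours.

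**The concern.** The Section 12.1.3 scale is meant for events that the table does not identify, yet the table has a row wide enough to take in every clinical event. If that row counts as identifying an event, the Section 12.1.3 scale never applies. If it does not, the row has no use. The protocol does not choose.

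The choice matters because the row sets a higher bar for Grade 3. Two people at the site, both following the protocol, could look at the same disabling event and differ on whether to halt enrollment or withhold a boost. This is a first-in-human trial whose primary objective is safety, and grading is done at the site as data arrive, so a later analysis document cannot settle it.

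The events are foreseeable. Section 1.1 reports chills and joint pain with an earlier Ad26 vaccine at the dose used here, without giving their grade. At twice that dose, moderate to severe chills came 12 to 18 hours after the first injection, which falls within the 24-hour gate between cohorts.

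**Working it through.** **1. The two scales side by side.** Cross activity (no interference, some, prevented) with medical intervention (not needed, needed). Here *some* means more than minimal interference.

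| Activity | Intervention | Section 12.1.3 | Attachment 1 catch-all row |
|---|---|---|---|
| None | No | 1 | 1 |
| None | Yes | 1 | 1 |
| Some | No | 2 | 2 |
| Some | Yes | 2 | no grade |
| Prevented | No | 3 | no grade |
| Prevented | Yes | 3 | 3 |

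The scales agree in 4 of 6 cells. In the other 2 the row gives no grade. The fifth line is the one that matters for Section 11.8.

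**2. Events affected.** Section 9.3.2 lists 6 local terms (erythema, induration, swelling, pain/tenderness, itching, warmth) and 9 systemic terms besides temperature (fatigue, headache, myalgia, arthralgia, chills, nausea, vomiting, rash, general itching), so 6 + 9 = 15. Six have no named row in Attachment 1: injection-site itching, warmth, arthralgia, chills, rash and general itching. It is five if general itching is placed under the mild grade of the allergic reaction row. Unsolicited events without a named row are affected too. Events with named rows, graded laboratory values, serious adverse events, deaths and anaphylaxis are not affected.

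**3. Internal comparison.** For fatigue and myalgia, Attachment 1 makes prevention of daily activity sufficient for Grade 3, with no intervention needed. Under the catch-all row, chills or arthralgia of equal impact would not reach Grade 3.

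**4. Check of the method.** The protocol gives no figure for severity grading. Its nearest figures are in Section 11.2, and 1 − (1 − p)^15 reproduces Table 11: 14.0%, 31.6%, 53.7%, 79.4% and 96.5%, against the printed 14, 32, 54, 79 and 96%. The upper limit for 0 of 15 is 1 − 0.025^(1/15) = 21.8%, matching the stated limit of less than 22%.

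**5. Illustration on assumed rates.** Let p be the chance per active subject of a related, activity-preventing event without a named row, and q the share of those needing medical intervention. Section 12.1.3 counts events at rate p. The row, if its ungraded events are treated as not Grade 3, counts them at rate p × q. The protocol gives neither p nor q.

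*One-subject rule.* Active subjects in Cohort 1 over the four groups: 4 + 5 + 4 + 5 = 18. Only events known by the gate count. P(at least 1) = 1 − (1 − rate)^18.

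| p | Section 12.1.3 | Row, q = 50% | Row, q = 25% |
|---|---|---|---|
| 1% | 17% | 9% | 4% |
| 2% | 30% | 17% | 9% |
| 5% | 60% | 37% | 20% |

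*Two-subject rule, unsolicited events only.* Active subjects in the main study: 4 × 15 = 60. Here p refers to the whole period the rule covers, so it need not equal the p above. P(at least 2) = 1 − (1 − rate)^60 − 60 × rate × (1 − rate)^59.

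| p | Section 12.1.3 | Row, q = 50% |
|---|---|---|
| 1% | 12% | 4% |
| 2% | 34% | 12% |
| 5% | 81% | 44% |

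The two definitions give the same probabilities only if q = 100%.

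**The case against.** The best defence is that the texts can be read together. The row and Section 12.1.3 never assign two different grades to the same cell; in the disputed cells the row is silent. An event that fits no cell can fairly be called not identified in the table, and Section 12.1.3 then supplies the grade. More simply, *not identified* may just mean having no row of its own, and study-specific body text may be expected to prevail over a general table. Both readings give the stricter result.

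These readings are sensible, but the protocol states neither. A site that applies the row literally would not call a disabling chill Grade 3, because a condition of Grade 3 is missing.

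Other points stand in part:

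- The illustration rests on assumed rates and counts ungraded events as not Grade 3.
- It ignores co-occurrence. A subject disabled by chills may also have disabling myalgia or fatigue, which have named rows and would trip the rule anyway, so the true difference is probably smaller.
- The moderate to severe chills were seen at twice the study dose and resolved within 24 to 36 hours. Section 3.2 describes Ad26 vaccines as generally well tolerated up to the study dose. The cohort gates are therefore more exposed than the 48-hour boost rule.
- Activity-preventing itching or warmth at the injection site is unlikely; chills, arthralgia and unsolicited events are the realistic cases.
- The investigator may suspend vaccination by judgment under Section 11.8. That is a useful backstop, but it does not replace a fixed rule.
- CRF guidelines that are not shown may give grading instructions; that cannot be checked here.

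**Conclusion.** The concern holds. For events without a named row, the protocol contains two Grade 3 definitions that differ by one condition, medical intervention, and no rule of precedence. The pausing and boost rules inherit the ambiguity. This follows from the text alone and rests on no assumed rate; the trip probabilities only show that the choice could matter. The scope is limited to events without a named row, and no sample-size figure is affected. It should be fixed, because it concerns a safety rule applied on site in real time.

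Attachment 1 also has minor slips below Grade 3. Low-potassium Grade 1 is printed with the upper instead of the lower limit of normal, QTc increases above 50 and below 60 ms have no grade, and some Grade 1 and Grade 2 laboratory ranges share a boundary value. They do not bear on the main point.

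**What to change.** State in Section 12.1.3 that every adverse event without its own named row in Attachment 1 is graded by the Section 12.1.3 scale, and that the All other conditions row does not apply. Alternatively, remove the medical-intervention wording from Grades 2 and 3 of that row.

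The cost is one sentence, or two deletions, plus matching CRF grading guidance; no procedures are added. The small downside is that the pausing rules may trip somewhat more often.

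In the same edit, start low-potassium Grade 1 from below the lower limit of normal (<LLN-3.1), extend the Grade 2 QTc increase to 30-59 ms, and make the shared Grade 1/2 laboratory boundaries mutually exclusive.
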